Intraoperative electrically-evoked auditory brainstem response (EABR) testing is undertaken to provide electrophysiological information concerning device placement and functionality. The primary electrode montage for EABR testing is midline, with the non-inverting electrode at Cz (vertex), the inverting electrode at C7 (cervical vertebra 7), and the ground electrode at the nape-of-neck (hairline). A discretionary duplicate set of electrodes can also be placed with the non-inverting electrode at Fz (high forehead), the inverting electrode anterior to the tragus on the ear contralateral to the surgical side, and the ground electrode at Fpz (mid-eyebrows). In all cases, electrodes are 15-20 mm subdermal needle electrodes sutured in place or

otherwise fixed with tape. All electrode leads are labeled, braided together, and positioned away from the surgical field with their terminals accessible. Electrode placement necessarily occurs during the preparation of the patient for surgery, and it is recommended that the impedances of the electrodes be measured at the time of placement to ensure optimum connectivity.

Following device placement, a series of bipolar stimulations are undertaken in an effort to elicit auditory-evoked responses. In general, initial electrode pairings for bipolar stimulation are transverse across the length of the device (see schematic of electrode pad in Figure 1b), with subsequent pairings honing in on more spatially localized stimulation, as dictated by the pattern of results and available testing time. The objective is to grossly map out the regions of the electrode pad that are conducive to auditory stimulation. This mapping allows interpretation in terms of placement/orientation of the electrode pad relative to the surface of the cochlear nucleus, and may guide device re-positioning decisions.

Stimulation parameters for this mapping process are optimized for auditory-evoked responses. Typical parameters include biphasic pulses (150 μ Sec/phase) presented at a rate of 35 Hz at a level of at least 150 CUs. When responses are observed, pulse polarity should be reversed to confirm the neural basis (see sample traces in Figure 1b). Stimulation is provided through the NRT Nuclear Response Telemetry system from Cochlear Ltd. using the Portable Programming System (PPS). For this testing, the head coil is placed within a sterile sheath and positioned over the receiving antenna of the implant. The PPS is connected to a Sprint speech processor that is stimulated by the Nucleus programming software NRT 3.1. The PPS also provides a TTL trigger to synchronize the EABR recording system. These systems are approved for use as a part of the Nucleus 24 ABI System.

The recording parameters are optimized for EABR recording. Typical parameters include wideband recording filters (e.g., 100 – 5000 Hz), 10-mSec recording window, amplifier gain of X100,000 with artifact rejection turned off. Number of averages is dictated by the quality of the response and is typically set to 500-1000.

Surgical Closure

Once the array is optimally placed, the dura will be closed with interrupted sutures. As the closure cannot be completely watertight owing to the cable from the array, abdominal fat may be harvested and used to create a watertight closure. The bone flap if present can be replaced with titanium mesh and screws or a complete mesh cranioplasty may be placed.

Postoperative Care

Following surgery, the child will be admitted to a specialized pediatric intensive care unit (PICU) in the North Carolina Children's Hospital. The unit is staffed full time by pediatric intensive care specialists with expertise and experience in pediatric neuro-intensive care. The child is monitored continuously using both invasive and non-invasive methods as needed. These may include an arterial line, central venous pressure (CVP) line, urinary catheter, blood pressure, pulse oximetry, EKG, and continuous nursing observation. It is anticipated that the child's endotracheal tube will be removed early in the postoperative period, either in the operating room or while in the PICU. Ventilator support as well as pain control and adequacy of sedation will be

closely monitored while an endotracheal tube is indwelling. Intravenous antibiotics will be administered for a no more than 24 hours following surgery in accordance with current recommendations from the American Association of Neurological Surgeons (AANS) and the American College of Surgeons (ACS). If the patient is allergic to penicillin or the cephalosporins, vancomycin will be administered intravenously for 24 hours. The pharmacy will be consulted for specific dosing based on the patient's weight. Corticosteroids will be administered for approximately 2 weeks or less following the surgery to minimize any brains swelling. Pain medication will be given prophylactically early on and as needed in the post-operative period. A CT scan will be obtained on the first postoperative night to evaluate for brain swelling and electrode array location (Figure 2 example). The patient in mobilized, and diet is advanced on the first postoperative day as tolerated. Intravenous fluids are weaned as oral intake increases.

The child is discharged from the PICU to a standard pediatric surgical floor no sooner than postoperative day 1 (day after surgery) or later as medically indicated. De-intensification includes removal of the urinary catheter, and discontinuation of continuous EKG and oximetry monitoring. On day 3 following surgery, the incision will be examined for CSF leakage. In the absence of a leak, the child will be discharged home with instructions for the parents to follow-up in one week as an outpatient. Appropriate phone numbers are provided for the clinics, hospital, and emergency department as well as details that should prompt the family to return to the hospital. These would include: increasing pain, swelling, nausea, vomiting, fever, shortness of breath, rapid breathing, changes in mental status, or anything that concerns the parents.

Should the child develop CSF leakage from the wound, over-sewing will be carried out as a sterile procedure. Should the child develop rhinorrhea, surgical re-exploration of the wound or lumbar subarachnoid drainage will be undertaken depending on the age and cooperativeness of the child and the presence and violation of the mastoid air cells that were observed at the time of surgery.

Initial Activation and Follow Up Testing

At the initial stimulation and at subsequent device programming sessions, a combination of objective data and behavioral methods will be used to program the speech processors. Data gathered from intra-operative electrophysiological testing that identified electrodes with optimal responses to stimulation would be selected for inclusion in the speech processor program. As with the initial stimulation of CIs in young children, behavioral observation and conditioned behavioral audiometry techniques will be used to determine electrical thresholds and comfortable listening levels. The initial stimulation will take place in the ENT clinic with pediatric anesthesia support. Starting with electrode pairs that elicited the best, evoked responses in the OR, stimulation will commence in a conservative fashion, using an ascending approach, until a behavioral response is observed. It will be documented when stimulation awareness is observed. Depending on the child's level of cooperation, conditioning of that response will ensue. During the initial stimulation and subsequent programming sessions, the child will be trained to participate in device setting. If stimulation levels result in visible or aversive responses (facial contraction, throat tickle, cough, shoulder activation, extremity sensations) higher stimulation levels will not be attempted. Although young children who have no auditory experience are limited in their ability to provide feedback about stimulation, our team of pediatric CI

audiologists has extensive experience in monitoring behaviors and interpreting responses to auditory electrical stimulation from children as young as 9 months of age on a routine basis. It is anticipated that the programming of the speech processor for the ABI will be similar in practice to programming CIs using a progressive mapping approach which includes making incremental changes to current levels over time, allowing for comfortable adaptation to sound. Only programs that have been stimulated in the clinic will be programmed to the user speech processor. The children will be seen at the designated follow up appointments for device programming at 4 weeks post initial stimulation and at 3, 6, 12, 18, 24, 30, 36 months for mapping and assessment including behavioral audiometry and speech perception testing. A language assessment will be repeated at 6-month intervals.

Data and Analysis

A single-subject research design was chosen (in which each subject serves as their own control) in order to accommodate for the heterogeneity that is well known to characterize auditory prosthesis research. Post-operative evaluations will be conducted at the initial activation and at 1, 3, 6, 12, 18, 24, 30, and 36-month intervals post-activation. Blinding or masking procedures are not included in the design, as the presence/absence of a brainstem implant cannot be easily concealed from the device recipients and/or clinical investigators.

Data will include demographics, frequency of both major and minor complications as well as audiometric and speech and language data. The summary statistics will be reported on the various categorical (gender and complications) and continuous (age, audiological and speech perception, production and language scores) variables.

Baseline audiological and speech perception, production and language measures taken prior to ABI surgery will be compared to scores at each follow up interval within each subject. For subjects with no response on behavioral testing, a maximum score of 120 dB HL will be assigned at the test frequency as this represents maximum stimulus levels of the equipment. Pure tone average (PTA) is calculated using the thresholds from 500, 1,000, and 2,000 Hz. When speech perception testing is limited by short duration experience or young age, inattention, or the presence of significant comorbidities, these reasons will be recorded. When inability to complete the test is evident despite significant implant experience, the patient is assigned the value for chance correct responses for the appropriate test (i.e., 0% for open-set tests or 33% for ESP pattern-[P] perception tests). When a child advances out of a particular measure because of ceiling effects, then the next measure will be undertaken. For children able to perform a given speech perception measure(s) prior to ABI surgery, that measure(s) will be repeated at the initial post-operative visits to insure the same test comparisons exist. It will be assumed that children that are unable to perform closed set testing will not be able to perform open set testing at a given visit. Thus, scores on these tests will be assigned the value of “unable to test”.

Change values for each of the variables will be calculated by subtracting off baseline values when available. The mean percent change at the various intervals for each variable can be averaged (+/- SD) across the subjects. Comparison to baseline measures for significance testing will be made with 95% confidence intervals when possible. The chance that this is not possible exists because of the broad variation in ages and possible achievements with the device.

For speech perception, there is a developmental hierarchy that is required to evaluate the emergence of this skill over time. This will be tracked and plotted on a graph against similar children with normal hearing as well as those fitted with CIs with and without malformations for comparison (30, 50). This modified cumulative speech perception index in quiet (SRI-Q) will be created after Wang et al. (50) and Buchman et al (30) in an effort to simultaneously display the data from all tests in the speech recognition hierarchy as a function of time. ESP-P is considered easier than ESP-monosyllabic (M) words. CNC word scores then follow PB-k word scores. The measured percentage score for each test (0%–100% correct) is then hierarchically ranked and stacked in 100-point increments. These results are controlled for duration of device usage and age at implantation. Speech production and language data are reported as age-normed values and will be compared to children of a similar age with normal hearing as well as those using CIs.

It is anticipated that this pilot study will be used to demonstrate safety and give some idea regarding efficacy. However, a larger scale clinical trial will be needed beyond the pilot study to demonstrate surgical safety on a broader scale (across surgeons and institutions) and the utility of the device for the intended auditory benefits. Ten subjects should be a sufficient sample size to demonstrate safety. If the European data is correct regarding complication rates in children, a single CSF leak might occur in one subject and non-auditory side effects can be expected to occur in roughly 20% of children or 2 subjects in this study. This number seems to be a conservative and reasonably small number to demonstrate these effects. Non-auditory stimulation is not serious and can be programmed around with simple changes in device programming during activation. For speech perception and production, the within subject design should allow us to see some benefit from the device if effective. Since the children are deaf, any development of significant open or closed set perception (beyond patten perception) would be attributable to the device. Similarly for language outcomes although these will take longer time to develop. Thus, the safety numbers are the drivers in powering this study.

The data will be recorded in patient-specific binders on a case-by-case basis after each subject encounter. All data will be entered in to the secure, File Maker Pro, customized database for CI research housed in the Department of Otolaryngology-Head and Neck Surgery that is currently in use. The lead investigator will cross check the data prior to approval for review. The data will be exported by desired fields to an Excel spreadsheet (Microsoft) for further analysis. Statistics will be carried out using SPSS software. If needed, statistical consultation will be sought at the University TRACS or Odum Institute.

Study Endpoints

Study endpoints are based on the 3 specific aims. For safety, this will be determined on a case-by-case basis and any adverse events will be reviewed with the IRB and the data monitoring board (2 individuals appointed). Should the adverse events be deemed unacceptable to the investigators, the IRB, or the monitoring board, this would be sufficient terms for study discontinuation. Three years of follow up was chosen to provide adequate time for the emergence of open-set speech perception abilities in the pre-lingual cohort of children. In studies of prelinguistic children undergoing CI, at least 2 years of follow-up is needed to demonstrate emergence of these skills (23). If no open set perception is demonstrated at 3 years, this seems to be good evidence for a lack of benefit on this measure. In general, speech and language measures should track speech perception abilities. While the full emergence of these skills can take

somewhat longer to develop, it is anticipated that early emergence will be evident if speech perception is developing. While not anticipated, a clear lack of benefit from the device (such as no sound awareness) among multiple subjects would also be consideration for stopping the study. Study recruitment is expected to be slow at 1-3/year. This will not stop the study.

Human subject protection measures

Risks and measures to minimize risk. There is limited psychological, social, legal and economical risk to patients for participating in this study. The potential for a confidentiality breach is rare. All children and their parents will be treated confidentially according to HIPAA and its requirements. All discussion of the results of the intervention for the purposes of results reporting will be made anonymously.

The physical risks include medication side effects, pain, discomfort, or injury from participation. The potential risks from participation are likely (10-25%) and dependent on the consequences in question. The potential complications have been detailed above.

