The following speech perception measures are routinely used with CI recipients and represent a hierarchy in both the child's required response and the difficulty of test material. When a child is not able to participate in structured testing for any reason including age, attention, or level of auditory development, then a parental questionnaire is used (IT-MAIS or MAIS). The earliest developmental response format is detection and imitation (LING 6-sound test), followed by a small (4 items) closed-set format (ESP-low-verbal) and then a larger (12 items) closed-set format (ESP standard). Open set speech recognition follows (PB-k, MLNT, LNT). Each child will be assessed starting with the lowest level of the battery at each assessment interval until a 100% score is achieved at 2 consecutive test intervals. Criteria for moving on to the next test are based on the child's developmental (behavioral and auditory) skills, not chronological or hearing age.

Meaningful Auditory Integration of Sound (MAIS) and Infant-Toddler Meaningful Auditory Integration of Sound (IT-MAIS) (51, 52). The MAIS is a 10-item parent-report scale designed to evaluate developing auditory behavior in children ages 4 years and older. Parents rate how often their child engages in specific behaviors with regard to their child's bonding with the sensory device, auditory awareness, and the ability to derive meaning from sound. The IT-MAIS was developed for children younger than 4 years. While it shares the majority of questions with the MAIS, the IT-MAIS additionally explores vocal behavior of infants with their sensory device. The MAIS probes ten questions in a structured parent interview,

assessing the child's bonding with the sensory device, auditory awareness, and ability to derive meaning from sound in everyday situations.

Ling Six Sound Test (Ling, 2002/2003). The Ling Six Sound Test samples the child's ability to detect and identify speech sounds representative of the speech frequency spectrum (ah, oo, ee, sh, s, m). The test is administered live-voice.

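### Two unranked rules for a child who cannot be tested, and change scored only where a baseline exists, let the optional mean open-set change omit non-achievers or later achievers, with bias in either direction.

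*Combined protocol and SAP*

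**What the plan says.** Data and Analysis has three provisions for a child who cannot be tested on speech perception.

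- **Chance rule.** If the child cannot complete a test even with substantial implant experience, "the patient is assigned the value for chance correct responses for the appropriate test (i.e., 0% for open-set tests or 33% for ESP" pattern perception. The amount of experience that triggers this is not defined.
- **Label rule.** "It will be assumed that children that are unable to perform closed set testing will not be able to perform open set testing" at that visit. The next sentence reads "Thus, scores on these tests will be assigned the value of" and supplies the label *unable to test*. This rule has no experience condition.
- **Recorded reasons.** When "testing is limited by short duration experience or young age, inattention, or the presence of significant comorbidities, these reasons will be recorded". No score is attached.

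The same section then defines the summary: "Change values for each of the variables will be calculated by subtracting off baseline values when available", and "The mean percent change at the various intervals for each variable can be averaged" across subjects. It does not say how the label enters either step.

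Elsewhere, Audiological Assessment sets out a hierarchy in which closed-set tests come first and "Open set speech recognition follows (PB-k, MLNT, LNT"). The Protocol section lets children without a present or patent cochlea receive the ABI with no previous CI. Aim 2 is improvement in speech understanding over baseline.

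**The concern.** A child with long implant use who cannot do closed-set testing meets both the chance rule and the label rule. One gives 0% on open-set tests and the other gives no number. The plan does not say which prevails.

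The choice is not neutral, because being untestable is related to outcome. At follow-up, the children given the label are the poorest performers. If the label is treated as missing, they leave the mean and the average gain rises.

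At baseline, a child who has never had an implant cannot meet the experience condition, so the chance rule supplies no starting value. If that child later reaches open-set perception, there is no change score, a success leaves the mean, and the average gain falls.

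Two analysts who both follow the text could therefore report different mean open-set gains from the same children. With about ten subjects, one or two omissions are enough to matter, and the study is meant to inform a larger trial.

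**Working it through.** **The plan's own figure.** There is none to reproduce. The plan gives no expected open-set score, standard deviation or power for this outcome. The check is therefore an illustration, and its child counts and scores are assumptions.

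**Inputs**
- N = 10, the total in the Protocol and in Methods and Subjects.
- *a* children reach open-set perception, each scoring S (assumed). All others are truly at 0%.
- *f* non-achievers carry the label *unable to test* at follow-up (assumed).
- *m* achievers have no numeric baseline (assumed).
- Every available baseline is 0%, the plan's chance value for open-set tests.

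**Formulas**
- Everyone at the floor at both times: S·a / 10.
- Labelled children kept at 0%, achievers without a baseline omitted: S(a − m) / (10 − m).
- Labelled children also dropped: S(a − m) / (10 − m − f).

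**Main case: a = 2, S = 50, f = 3**

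| Handling | Calculation | Mean change (points) |
|---|---|---|
| All at the floor | 100 / 10 | 10.0 |
| 3 labelled children dropped | 100 / 7 | 14.3 |
| 1 achiever without baseline, the 3 kept at 0% | 50 / 9 | 5.6 |
| 1 achiever without baseline, the 3 dropped | 50 / 6 | 8.3 |

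**Sensitivity to f** (a = 2, S = 50, m = 0, labelled children dropped): f = 1 gives 100 / 9 = 11.1; f = 5 gives 100 / 5 = 20.0.

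**Net direction when both omissions occur** (a = 3, S = 40; all-counted mean 120 / 10 = 12.0):
- 1 achiever and 5 non-achievers omitted: 80 / 4 = 20.0, too high.
- 2 achievers and 3 non-achievers omitted: 40 / 5 = 8.0, too low.

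So the sign depends on the mix and cannot be predicted from the plan.

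**Relative change.** The plan's term is mean percent change. If that means relative change, the divisor is the baseline, and from 0% the result is undefined.

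**The case against.** **The two rules may be meant for different children.** The test hierarchy supports giving 0% to a child working at open-set level and the label to a child below it. That is plausible, but the plan does not say so. Under that reading, the lowest performers are exactly the ones left without a number.

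**Late visits are probably covered.** After 36 months of ABI use the chance rule is the natural one, and it keeps non-achievers at 0%. This stands: the upward bias belongs mainly to earlier visits. It also needs at least one achiever at the visit, since with a = 0 every version of the mean is 0. No cut-off can be placed, because the required experience is undefined.

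**Most baselines should exist.** A reader might set the 18-month age limit beside the ESP's usual introduction at about 2 years and infer that missing baselines will be common. The documents do not support that. Inclusion Criteria says children of 18 months can be tested with the standardized measures, and requires at least 6 months of CI use where a cochlea is present or patent. Exclusion Criteria delays the ABI when inability to take part looks age-related. What remains is chiefly the subgroup with no previous CI. Its size is not given, and that exclusion is worded for testing with a CI.

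**The SRI-Q.** A reader might infer that this index is biased too, because each score "is then hierarchically ranked and stacked in 100-point increments" and the label has no score. That is not shown. A stacked index can leave the child on the closed-set rung, and its construction is deferred to two cited papers.

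**A spurious ESP gain.** A reader might also infer a false gain of 33 points on ESP pattern perception, from an untested baseline of 0 to a chance value of 33%. The plan never assigns a 0 on that test, so this does not follow.

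**Conclusion.** The point holds in limited form. The plan has no single numeric rule for open-set inability, so an across-child mean of open-set change can be too high or too low depending on which children drop out. In the main illustration, 10.0 points becomes 14.3 or 5.6. This rests on assumed counts and scores, on zero baselines, and on the label being treated as missing. The downward direction does not depend on how the two rules are reconciled; it needs only an achiever with no numeric baseline.

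A reader might go further and infer that the efficacy findings as a whole are unreliable. The documents do not support that. The mean is optional, and the plan itself warns that comparison with baseline may not be possible given the spread of ages and abilities. The main comparison is within each child. The 3-year judgement in Study Endpoints asks whether open-set perception has appeared, which needs no mean change. Safety drives the sample size. The gap is worth closing because it is cheap to close, not because the study's conclusions turn on it.

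**What to change.** Amend Data and Analysis as follows.

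1. For open-set change scores, use 0% at baseline and at follow-up for every child recorded as unable to test or not advanced to open-set testing. Keep the label as a recorded reason.
2. Where the recorded reason is young age, short experience, inattention or comorbidity, that reason takes precedence over item 1. Flag the visit and show the mean twice, with flagged visits at 0% and with them treated as missing, giving the number of children behind each mean.
3. Report open-set change in percentage points.
4. Report the number of children reaching open-set perception out of all implanted, with an exact 95% interval. For example, 2/10 is 20%, interval 2.5% to 55.6% (Clopper-Pearson). This result does not depend on a baseline score.

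The cost is a few sentences of analysis text and a little extra tabulation, with no new visits or tests. Reported mean gains may become smaller, because failures stay in at 0%, or larger, because achievers without a baseline come back in. Floor-scoring a very young child at baseline can count maturation as device gain; the paired results in item 2 make that visible.
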